## 5.6 Supportive Care

Subjects should receive appropriate supportive care measures as deemed necessary by the site investigator. Suggested supportive care measures for the management of adverse events with potential immunologic etiology are outlined below. Where appropriate, these guidelines include the use of oral or intravenous treatment with corticosteroids as well as additional antiinflammatory agents if symptoms do not improve with administration of corticosteroids. Note that several courses of steroid tapering may be necessary as symptoms may worsen when the steroid dose is decreased. For each disorder, attempts should be made to rule out other causes such as metastatic disease or bacterial or viral infection, which might require additional supportive care. The treatment guidelines are intended to be applied when the investigator determines the events to be related to Durvalumab.

Early recognition of signs and symptoms potentially related to an inflammatory or immunemediated mechanism is important for proper management of toxicities. For guidance on identifying, evaluating, and treating imAE, see the Toxicity Management Guidelines in Appendix A.

ImAE observed with anti PD-L1/PD-1 agents may include pneumonitis, hepatitis, diarrhea/colitis and intestinal perforation, endocrinopathies (hypo- and hyper-thyroidism, adrenal insufficiency, hypophysitis/hypopituitarism and Type 1 diabetes mellitus), nephritis, rash/dermatitis, pancreatitis, myocarditis, myositis/polymyositis and rare/less frequent imAE including neuromuscular toxicities such as myasthenia gravis and Guillain-Barre syndrome.

Other inflammatory responses that are rare with a potential immune-mediated etiology are also considered as imAE and include, but are not limited to, pericarditis, sarcoidosis, uveitis and other events involving the eye, skin, hematological and rheumatological events. It is possible that events with an inflammatory or immune mediated mechanism could occur in nearly all organs.

In addition, infusion-related reactions and hypersensitivity/anaphylactic reactions with a different underlying pharmacological etiology are also considered imAEs (Durvalumab IB).

For guidelines on the treatment of immune-mediated adverse events, please refer to the published ASCO guidelines [14].

## 5.7 Reproductive Information

Participants of childbearing potential who are sexually active and their partners must agree to abstain from heterosexual intercourse or to use 2 forms of effective methods of contraception beginning with time of consent (females) or prior to C1D1 treatment (males), during the study treatment and for 90 days after last dose of durvalumab (or timeframe outlined per package insert for chemotherapy or institutional guidelines for radiation). Two contraception methods can be comprised of two barrier methods, or a barrier method plus a hormonal method. See below for options:

Acceptable non-hormonal birth control methods:

- Total sexual abstinence ie, refrain from any form of sexual intercourse in line with the patients' usual and/or preferred lifestyle. Abstinence must be for the total duration as described above. Periodic abstinence (eg, calendar ovulation, symptothermal, postovulation methods) and withdrawal are not acceptable methods of contraception.
- Vasectomised sexual partner PLUS male condom. With participant assurance that partner received post-vasectomy confirmation of azoospermia.
- Tubal occlusion PLUS male condom
- Intrauterine Device (IUD) PLUS male condom. IUD coils should be copper-banded.

Acceptable hormonal methods:

- Etonogestrel implants (eg, Implanon®, Norplant®) PLUS male condom
- Normal and low dose combined oral pills PLUS male condom
- Hormonal shot or injection (eg, Depo-Provera) PLUS male condom
- Intrauterine system device (eg, levonorgestrel-releasing intrauterine system -Mirena®) PLUS male condom

Female subjects should not breastfeed during treatment and for at least 3 months after the last dose of durvalumab (or timeframe outlined per package insert for chemotherapy or institutional guidelines for radiation).

Male subjects should not donate sperm during treatment and for at least 3 months after the last dose of durvalumab (or timeframe outlined per package insert for chemotherapy or institutional guidelines for radiation).

## 6. TOXICITIES AND DOSE DELAYS/DOSE MODIFICATIONS

The NCI Common Terminology Criteria for Adverse Events (CTCAE) v5 will be used to grade adverse events.

Subjects enrolled in this study will be evaluated clinically and with standard laboratory tests before and at regular intervals during their participation in this study as specified in Study Calendar & Evaluations.

Subjects will be evaluated for adverse events (all grades), serious adverse events, and adverse events requiring study drug interruption or discontinuation as specified in Study Calendar & Evaluations.

### 6.1 Dose Delays/Dose Modifications

#### 6.1.1 Induction Durvalumab

Dose reductions of durvalumab with induction therapy will not be permitted. See Appendix A for toxicity management guidelines.

#### 6.1.2 Chemoradiation

Chemoradiation should not be initiated until any toxicity attributed to induction durvalumab has resolved to  $\leq$  Grade 1. If initiation of chemoradiation is delayed  $\geq$  1 week beyond the planned initiation date secondary to toxicity from durvalumab induction therapy, the HCRN Project Manager and sponsor-investigator should be notified.

Dose reductions or delays of chemotherapy and/or radiation based upon toxicities from chemotherapy or radiation will be conducted per institutional standard of care at the discretion of the treating investigator.

Chemotherapy doses held during chemoradiation should not be added after completion of radiation.

#### 6.1.3 Consolidation Durvalumab

Dose reductions of durvalumab during consolidation therapy will not be permitted. See Appendix A for toxicity management guidelines.

### 6.2 Protocol Therapy Discontinuation

In addition to discontinuation from therapy related to toxicities as outlined above, a subject will also be discontinued from protocol therapy and followed per protocol under the following circumstances outlined below. The reason for discontinuation of protocol therapy will be documented on the electronic case report form (eCRF).

- Documented confirmed disease progression. In the absence of clinical deterioration, if disease progression is identified per RECIST 1.1, confirmatory scan should be performed no earlier than 4 weeks after the initial assessment of progressive disease. Study drug administration may continue between these assessment scans in the absence of prohibitive toxicity, and the patient must continue to meet eligibility criteria. Patients with rapid clinical deterioration or rapid disease progression will not be eligible to continue treatment and will be discontinued from therapy.
- Subjects who fall to  $\leq 30$  kg.
- Site investigator determines a change of therapy would be in the best interest of the subject
- Subject requests to discontinue protocol therapy, whether due to unacceptable toxicity or for other reasons
  - o In a subject decides to prematurely discontinue protocol therapy (“refuses treatment”), the subject should be asked if he or she may still be contacted for further scheduled study assessments. The outcome of that discussion should be documented in both the medical records and in the eCRF.
- Female subject becomes pregnant
- Protocol therapy is interrupted for  $\geq 6$  weeks.

### 6.3 Protocol Discontinuation

If a subject decides to discontinue from the protocol (and not just from protocol therapy) all efforts should be made to complete and report study assessments as thoroughly as possible. A complete final evaluation at the time of the subject's protocol withdrawal should be made with an explanation of why the subject is withdrawing from the protocol. If the reason for removal of a subject from the study is an adverse event, it will be recorded on the eCRF.

## 7. STUDY CALENDAR & EVALUATIONS

Induction and Consolidation: Cycle = 28 days	Screen	Induction	Chemoradiation	Consolidation	Safety follow up visit 	Long-term Follow up 
	-28 days	Cycle 1		Day 1 ± 3	Cycle 1-12	Every 3 months (±14days)
		Day 1 ± 3				
REQUIRED ASSESSMENTS						
Informed Consent	X					
Medical History 	X					
Diagnosis and Staging 	X					
Physical Exam 	X	X	X 3	X	D30	
Vital signs and ECOG Performance Status 	X	X	X 3	X	D30	
ECG	X					
AEs & concomitant medications	X	X	X 3	X	X	
LABORATORY ASSESSMENTS						
Complete Blood Cell Count with diff (CBC)	X	X 13	X	X	D30	
Comprehensive Metabolic Profile (CMP)	X	X 13	X	X	D30	
PT/INR and aPTT	X					
Thyroid Function Testing 	X			X 5		
Pregnancy test (serum or urine) (WOCBP) 	X	X 6		X 6		
DISEASE ASSESSMENT						
CT of chest 	X			X 7	X 7	X 7
CT or MRI of abdomen and pelvis 				X 7	X 7	X 7
MRI or CT Brain 	X			as clinically indicated		
PET Scan 	X 7			as clinically indicated		

TREATMENT EXPOSURE						
Durvalumab		X		X		
Chemoradiation per standard of care			X			
SPECIMEN COLLECTION						
Archival Tumor Tissue 	X					
Blood Samples 		C1D1		X 9		
Stool Microbiome 		X 10				
FOLLOW-UP						
Survival Status, Subsequent Therapy						X

Key to Footnotes

1: Medical History; other data to be obtained during this assessment includes: (1) a smoking history questionnaire, (2) trial awareness question (3) documentation of prior anti-cancer treatment including medications (chemotherapy, checkpoint inhibitors, etc) radiation or surgery and (4) If prior genetic testing has been done those results should be made available.

2: Diagnosis and Staging to include pathology report and staging documentation. AJCC version 8 will be used for recording of staging.

3: Patients should have weekly physical exam and vital signs per good medical practice during chemoradiation. AEs and concomitant meds should be recorded weekly during chemoradiation.

4: Vital signs to include temperature, pulse, respirations, blood pressure, weight, and height (screening only) and ECOG performance status. Patients will be monitored before, during and after the durvalumab infusion with assessment of vital signs. Patients are monitored (pulse rate, blood pressure) every 30 minutes (- 5 minutes/+ 10 minutes), during the infusion period (including times where infusion rate is slowed or temporarily stopped).

5: CBC with differential and platelet to include: WBC, ANC, Hgb, Hct, PLT. CMP to include sodium, potassium, chloride, creatinine, blood urea nitrogen; liver function tests (LFTs) to include AST, ALT, total bilirubin, alkaline phosphatase. Thyroid Function testing should be performed at

screening, at start of consolidation durvalumab, then every 3 cycles during consolidation durvalumab. TSH will be obtained. T4 and T3 including free versus total testing is at the discretion of the site investigator.

6: For women of childbearing potential (WOCBP): urine or serum  $\beta$ hCG will be done at screening and within 24 hrs of 1st dose of study drug. During treatment with consolidation durvalumab, a pregnancy test should be performed every 4 weeks. If a urine test is done and it is positive or cannot be confirmed as negative, a serum pregnancy test will be required.

7: Tumor assessments to be performed at (1) screening (PET scan may be within 42 days prior to C1D1) (2) within 0-24 days after completion of chemoradiation/prior to C1D1 of consolidation durvalumab, then every 3 months (about every 3 cycles/ $\pm$  7 business days) during consolidation durvalumab. Screening tumor assessment will consist of evaluation by CT scans of chest (contrast enhanced), PET scan, and contrast-enhanced MRI or CT of the brain. Response assessment imaging will include CT scans of chest, abdomen, and pelvis (contrast enhanced). MRI or CT brain or PET scan after screening should be performed as clinically indicated. Imaging selected for each subject should remain the same throughout the study. Tumor imaging at treatment discontinuation/D30 safety follow up visit is at discretion of site investigator. If tumor assessments are available for subjects who have not yet experienced progressive disease (PD) at the time treatment is discontinued, the follow-up tumor evaluations will be documented in the eCRF until PD or death is confirmed, or until another treatment is initiated. A window of 7 days may be applied to obtain scans.

8: Archival tissue is required if available and should be identified at screening and shipped prior to chemoradiation. PD-L1 testing may be performed using either 22C3 or SP263 testing per the institution's standard of care. If not performed via the treating institution, PD-L1 testing to be performed through the Providence Cancer Institute, using in-house SP263 assay pending the availability of funding. Tumor Mutation Burden testing and multispectral IHC will also be performed pending the availability of funding.

9: Peripheral blood will be collected for serum, plasma, and peripheral blood mononuclear cells (PBMCs). Timepoints include (1) prior to Cycle 1 Day 1 (C1D1) induction durvalumab, (2) prior to C1D1 consolidation durvalumab, and at (3) 8 weeks after starting consolidation durvalumab (prior to Cycle 3 Day 1 consolidation durvalumab). Immune monitoring testing and ctDNA analysis will be collected. Analysis to be performed pending the availability of funding. Subjects will be consented for optional storage of any remaining tissue/blood samples collected prior to C1D1 treatment after protocol-specified studies are complete. These samples will be stored for future unspecified cancer-related research and are considered "banking samples".

10: Stool for microbiome analysis will be performed prior to treatment C1D1. Subjects will be provided a kit with detailed instructions regarding collection of the sample prior to the timepoint it is due. Analysis will be performed pending the availability of funding. Please see the CLM for additional details.

11: The safety follow-up visit should only occur when subjects permanently stop study treatment for whatever reasons (toxicity, progression, or at discretion of site investigator) and should be performed 30 days ( $\pm$  7 days) and 100 days ( $\pm$  7 days) after the last dose of treatment. More frequent follow up for management of toxicity will be per institutional standard of care and the treating investigator. Subjects who have an ongoing Grade  $\geq$  2 or serious AE (SAE) at this visit will continue to be monitored by a member of the study team until the event is resolved, stabilized, determined to be irreversible by the site investigator or until a new anti-cancer treatment starts, whichever occurs earlier. The D100 evaluation may be completed via phone call.

12: After the D100 safety visit, subjects who discontinue treatment for any reason without documented disease progression will be followed for disease progression every 3 months up to 12 months after initiation of consolidation durvalumab. Once disease progression is documented, subjects will enter a survival follow up period every 6 months for 1 year from the time of documented progression or until 1 year after initiation of consolidation durvalumab. Follow up may be accomplished via clinic visit, phone call, or other avenues as appropriate. A window of  $\pm$  14 days will be applied to follow up.

13: If screening (baseline) CBC and CMP were performed within 7 days of Day 1 of treatment, these do not need to be repeated. All laboratory assessments should be done prior to treatment.

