#### 2.1.3 Correlative/Exploratory Objectives

- Correlation of outcomes and toxicity based upon tumor and immune cell PD-L1 status in baseline tumor biopsy prior to therapy.
- Correlation of toxicity based upon type of chemotherapy administered.
- Correlation of outcomes based upon tumor mutation burden in baseline tumor biopsy prior to therapy.
- Assessment of immune response via peripheral blood immune monitoring through multiple timepoints of therapy.
- Correlation of immune response with outcomes in terms of disease control and toxicity.

- Correlation of tumor immune score via quantitative multiplex tumor biopsy assay with clinical outcomes.
- Exploration of immune response signal to indicate further exploration of a treatment schedule in a larger trial.
- Collection of microbiome samples to correlate with outcomes and toxicity.

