Samples for immunological monitoring will include blood (including for circulating tumor DNA analysis), archival tumor tissue, and collecting peripheral blood mononuclear cells (PBMC) and serum. The main objectives of the monitoring will be to characterize circulating T-cell subsets and changes in the tumor microenvironment (TME) following treatment that may correlate with clinical responses.

Flow cytometry analysis with a panel of markers including CD3, CD4, CD8, CD25, CD127, CCR7, FoxP3, ICOS, and CD45RA will be performed. T cell sub-populations of interest include effector, regulatory T cell ( $T_{reg}$ ), central memory, and effector memory cells. Other immunological measures may be evaluated including, but not limited to, immunohistochemistry analysis of biopsy samples and measurement of serum cytokine levels using multiplex ELISA (Luminex assay) to generate hypotheses for future studies and to gain insight into possible biomarkers of response.

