### 8.2.1 Serum

Specimens for serum will be collected prior to C1D1 induction durvalumab; prior to C1D1 consolidation durvalumab; and at 8 weeks after consolidation durvalumab (prior to Cycle 3) for immune monitoring analysis. All specimens should be collected prior to drug administration.

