### 8.2.2 Peripheral Blood Mononuclear Cells (PBMCs)

Specimens for PBMCs will be collected prior to C1D1 induction durvalumab; prior to C1D1 consolidation durvalumab; and at 8 weeks after consolidation durvalumab (prior to Cycle 3) for immune monitoring analysis. All specimens should be collected prior to drug administration.

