### 8.2.3 ctDNA

Specimens will be collected prior to C1D1 induction durvalumab; prior to C1D1 consolidation durvalumab; and at 8 weeks after consolidation durvalumab (prior to Cycle 3) for circulating tumor DNA analysis.

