### 12.6.3 Analysis Plans for Exploratory Objectives

To assess the immune response via peripheral blood immune monitoring through multiple time points of therapy, the patterns of change will be described using descriptive statistics and plots of means (standard deviation) as well as quantiles over time. Additionally, longitudinal data analysis will be employed to calculate the trajectory of change between repeated measures. Various variance-covariance structures will be explored to obtain an efficient model. We will also perform repeated measures ANOVA to test for a time by intervention interaction.

To evaluate the association between outcomes and predictors, controlling for other risk factors, we will perform linear regression analysis for continuous outcome; logistic and ordinal logistic regression analyses for binary and ordinal outcomes, respectively.

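### The time-by-intervention test of the immune data cannot be estimated in one arm, and the sampling times allow only a combined reading of induction plus chemoradiation

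*Combined protocol and SAP*

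**What the plan says.** **Analysis.** For the peripheral blood immune data, section 12.6.3 plans descriptive statistics, plots over time and a longitudinal analysis of the trajectory between repeated measures, with alternative covariance structures. It then adds: "We will also perform repeated measures ANOVA to test for a time by intervention interaction".

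**Design.** Sections 5 and 12.1 describe a single arm. Every patient is to receive one induction dose of durvalumab, then concurrent chemoradiation, then consolidation durvalumab.

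**Blood.** Study calendar footnote 9 sets three research draws: "prior to Cycle 1 Day 1 (C1D1) induction durvalumab, (2) prior to C1D1 consolidation durvalumab", and a third 8 weeks into consolidation. Sections 8.2.1 to 8.2.3 repeat these times for serum, PBMCs and ctDNA. The calendar's research blood row is empty under chemoradiation.

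**Tissue.** The introduction to section 8 gives as a main objective of the monitoring to characterize circulating T-cell subsets and "changes in the tumor microenvironment (TME) following treatment that may correlate with clinical responses". Footnote 8 and section 8.1.1 provide for archival tissue only, and section 8 places the multiplex immunohistochemistry on biopsies taken before treatment.

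**Purpose.** One exploratory objective in section 2.1.3 is "Exploration of immune response signal to indicate further exploration of a treatment schedule in a larger trial".

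**The concern.** An interaction between time and intervention asks whether the course over time differs between groups that did and did not receive something. This trial has no such groups. The plan commits to a test that cannot be run, or that software will run only by silently dropping terms, leaving a time effect that could be reported under the wrong name.

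Interpretation is also affected. Induction is the only element added to the standard of care described in section 1.2, and the immune signal is meant to inform a schedule for a larger trial. A shift between the first and second samples could come from induction, from chemoradiation, or from both. Unless the plan says this, a reader of the results could take such a shift as evidence about induction.

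The tissue aim has a similar problem: change in the microenvironment needs at least two tissue timepoints, and one is planned.

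**Working it through.** The plan states no sample size, power or effect size for immune monitoring, so there is no figure of its own to reproduce. The checks are structural.

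**1. Is the interaction estimable?**

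Inputs: three timepoints (footnote 9; sections 8.2.1 to 8.2.3) and one arm (sections 5 and 12.1). Let *g* indicate the intervention group. The mean model is

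b0 + b1·[t=2] + b2·[t=3] + c·g + d2·g·[t=2] + d3·g·[t=3], with 6 columns.

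Every patient has g = 1, so the column for g equals the intercept, g·[t=2] equals [t=2], and g·[t=3] equals [t=3]. Three columns are duplicates, so the rank is 6 − 3 = 3. Only the sums b0 + c, b1 + d2 and b2 + d3 can be estimated, that is, a mean at each time. With two groups the rank would be 6 of 6. Adding a further blood draw to one arm does not help.

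Reading *intervention* as treatment phase does not rescue the test, because phase coincides with time here. The plan's comparator for efficacy is the PACIFIC historical control, and no immune data from it are described.

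**2. What lies between samples 1 and 2?**

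- Induction dose to start of chemoradiation: 4 to 5 weeks, or 28 to 35 days (section 5).
- Radiation: 54 to 66 Gy at 1.8 to 2 Gy per fraction, 5 per week (section 5.2.2). Fewest fractions: 54 / 2 = 27. Most: 66 / 1.8 = 36.7, so 37.
- First to last fraction, starting on the first treatment day of a week: 27 fractions are 5 full weeks plus 2, so 5×7 + 1 = 36 days. 37 fractions are 7 full weeks plus 2, so 7×7 + 1 = 50 days.
- End of chemoradiation to consolidation: 1 to 42 days (section 5).

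Shortest gap: 28 + 36 + 1 = **65 days**. Longest on the same basis: 35 + 50 + 42 = **127 days**. This assumes that blood is drawn on the dosing days, that chemotherapy and radiation start together, and that there are no holidays, interruptions, delays or visit windows.

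**3. Can induction be separated from chemoradiation?**

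Exposure received by each sample:

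| Sample | Baseline | Induction | Chemoradiation | 8 weeks of consolidation |
|---|---|---|---|---|
| 1 | 1 | 0 | 0 | 0 |
| 2 | 1 | 1 | 1 | 0 |
| 3 | 1 | 1 | 1 | 1 |

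The induction and chemoradiation columns are identical: rank 3 for 4 parameters. Only their sum is estimable. A draw after induction and before chemoradiation would add the row 1, 1, 0, 0 and raise the rank to 4.

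**4. Tissue.**

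Section 8 speaks of change after treatment. Against that, the calendar schedules archival tissue at screening only, footnote 8's reference to chemoradiation is a shipping deadline rather than a new biopsy, and the immunohistochemistry uses pre-treatment material. There is one tissue timepoint, so change cannot be measured.

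**The case against.** The strongest reply is that the plan never undertakes to isolate induction. The blood objective in section 2.1.3 covers therapy as a whole across several timepoints, and the hypothesis in section 1.4 concerns the whole sandwich sequence. Three samples can describe change over that sequence. This stands: the absence of a draw between induction and chemoradiation contradicts no stated objective and is not an error.

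Some stronger readings are tempting, and the documents do not support them:

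- *That the plan credits a pre-consolidation change to induction.* No passage does so, and section 12.2.3 presents these analyses as descriptive and exploratory. The most that can be said is that the result could be misread.
- *That no usable analysis remains.* Section 12.6.3 already plans a longitudinal analysis, and the interaction test is an addition to it. Removing that sentence leaves a workable plan.
- *That no blood at all is taken in this period.* Safety CBC and metabolic panels are marked under chemoradiation in the calendar. Only research blood is absent.
- *That 127 days is a true maximum.* Section 5.2.2 allows interruptions and up to a week between the chemotherapy and radiation starts, and sections 5 and 6.1.2 contemplate late starts. The aliasing does not depend on the length of the gap.

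The tissue wording could also be called one loose phrase in a background section, since the listed tissue objectives refer to baseline biopsies. That limits its weight, but the phrase still describes something the planned collection cannot deliver.

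**Conclusion.** Wrong as written on two counts, both minor. The interaction test in section 12.6.3 is not estimable (rank 3 of 6), given one arm, one sequence and no control immune data. The aim of measuring microenvironment change in section 8 has no post-treatment tissue behind it.

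A limit on interpretation also needs to be stated. A change from sample 1 to sample 2 spans induction plus the whole of chemoradiation, about 65 to 127 days under the assumptions above, and cannot be divided between them. It is, besides, an uncontrolled before-after change.

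The consequences are confined to exploratory analyses whose assays depend on funding. The primary PFS and safety analyses do not change.

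**What to change.** In section 12.6.3:

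- Delete the time-by-intervention test.
- Keep the longitudinal model already planned and specify a time effect with two named within-patient contrasts: sample 2 versus sample 1, labelled *induction plus chemoradiation*, and sample 3 versus sample 2, labelled *first 8 weeks of consolidation*.
- State that the immune data cannot attribute change to induction alone.

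In section 8, limit the microenvironment aim to the baseline microenvironment and its association with outcome.

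These are wording changes. They need no new samples or visits.

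Optional, as a design suggestion and not a correction: a research draw after induction and before chemoradiation would make the change over the induction interval estimable, though still uncontrolled. It is more than one tube. Each existing timepoint supplies serum, plasma and PBMCs as well as ctDNA, so it would mean a fourth sample set and fourth round of assays when the present three depend on funding, with changes to the calendar, consent and laboratory manual. The calendar gives no day for the CBC and metabolic panel under chemoradiation, so a draw before the first chemoradiation dose would have to be scheduled explicitly.

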## 12.6 Data Analysis Plans

### 12.6.1 Analysis Plans for Primary Objective

The progression-free survival analyses will be performed considering the risk of dying from another cause before experiencing progression related events using the competing risk egression method (de Glas et al., 2016). Cumulative incidence functions will be displayed and summarized for the median time to progression as well as percentage of progression patients at 12, 18, and 24 months. In addition, competing risk regression will be used to estimate sub distribution hazard ratios of the study arm versus historical control arm and 95% confidence intervals, adjusted for patient demographic, clinical, pathological, and tumor related factors. To compare the overall survival between groups, Kaplan-Meier survival curves will be displayed and summarized. Survival curves will be statistically compared using the log-rank test. If the proportional hazards assumption is met, survival curves will also be compared using proportional Cox regression, adjusting for risk factors.

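### Footnote 12 ties survival follow-up to progression and leaves its end point open; if the one-year-from-progression limit is used, overall survival after about month 12 to 13.4 is biased low

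*Combined protocol and SAP*

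**What the plan says.** Footnote 12 to the Section 7 calendar sets long-term follow-up after the day-100 (D100) safety contact. Patients who have stopped treatment without progression "will be followed for disease progression every 3 months up to 12 months after initiation of consolidation durvalumab". Once progression is documented, "subjects will enter a survival follow up period every 6 months for 1 year from the time of documented progression", and the sentence goes on "or until 1 year after initiation of consolidation durvalumab". It does not say whether the earlier or the later limit governs, or whether the two limits serve different patients. In the calendar, the row "Survival Status, Subsequent Therapy" is marked only under long-term follow-up.

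Two other footnotes bear on progression-free patients. Footnote 11 sets a contact 100 days after the last dose ("The D100 evaluation may be completed via phone call"). Footnote 7 says that, if tumor assessments are available, "the follow-up tumor evaluations will be documented in the eCRF until PD or death is confirmed, or until another treatment is initiated", with no 12-month cap.

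Section 12.6.1 states: "To compare the overall survival between groups, Kaplan-Meier survival curves will be displayed and summarized". It adds a log-rank test and, if hazards are proportional, Cox regression. It gives OS no time origin, horizon or censoring rule. OS does not appear among the objectives and endpoints in Sections 2 and 12.2.

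**The concern.** Kaplan-Meier, log-rank and Cox methods all require that a patient censored at a given time has the same outlook as those still under observation. Progression is a strong predictor of death. If progression-free patients leave observation around month 12 while progressed patients are followed for a year after progression, the patients with the best outlook are removed and those with the worst remain. The later part of the curve then describes survival after progression rather than survival of the cohort.

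The error would make the regimen look worse than it is, and for given post-progression survival it grows as PFS improves. The trial exists to decide whether a randomized trial is worth running, so a falsely low OS curve could count against the regimen. Separately, because the governing limit is not stated, two sites could follow identical patients for different lengths of time.

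**Working it through.** **The plan's own figure.** The documents give no OS figure. The one related figure is the sample size of 49 in Section 12.3. With exponential PFS, the monthly hazards are −ln(0.559)/12 = 0.0485 and −ln(0.699)/12 = 0.0298, a hazard ratio of 0.616. Events needed: (1.645 + 0.842)² / (ln 0.616)² = 26.3. With 18 months of accrual and 12 more of follow-up, the event probabilities are 0.627 and 0.459, averaging 0.543. Then 26.3/0.543 = 48.4, so 49. This calculation follows PFS for 12 to 30 months per patient. Section 12.6.1 also asks for "percentage of progression patients at 12, 18, and 24 months". So the plan looks past month 12 in places, although not explicitly for OS.

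**When observation of progression-free patients ends.** Cycle 12 day 1 falls 11 × 28 = 308 days after consolidation starts. D100 is then day 408, and 408/30.44 = 13.4 months (13.2 to 13.6 with the ±7-day window). An on-schedule completer is therefore known alive at about month 13.4, already past footnote 12's 12-month limit, with no later scheduled contact.

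**Model for OS from the start of consolidation.** From the documents: 12-month PFS of 55.9% or 69.9%, and 49 patients. Assumed, not in the documents: exponential PFS with hazard λ; a share q = 5% or 15% of PFS events being deaths without progression; exponential post-progression survival with median m = 9, 15 or 24 months, hazard μ = ln 2/m.

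True survival: S(t) = e^(−λt) + (1−q)·λ/(μ−λ)·(e^(−λt) − e^(−μt)).

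If progression-free patients stop at month c and progressed patients continue to progression + 12 months, everyone at risk after c has progressed and has hazard μ. Kaplan-Meier then converges to S(c)·e^(−μ(t−c)).

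**One case by hand** (PFS 69.9%, m = 14, q = 0, c = 12). λ = 0.0298 and μ = 0.0495. S(12) = 0.922 and true S(18) = 0.849. Kaplan-Meier at month 18 = 0.922 × e^(−0.0495 × 6) = 0.922 × 0.743 = 0.685, which is 16.4 points too low. At month 12 the bias is zero.

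**Range over the assumed scenarios** (simulation, 400,000 patients each; the closed form agrees to about 0.3 point):

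| How footnote 12 is applied | Bias at month 12 | Bias at month 18 | At risk at month 18, of 49 |
|---|---|---|---|
| Progression + 12 months; progression-free stop at month 12 | 0 | −5.5 to −22.9 points | 2.9 to 6.7 |
| Same, crediting D100 at month 13.4 | 0 | −4.1 to −18.1 points | 3.7 to 8.2 |
| One year after the start of consolidation for all | 0 | not estimable | 0 |

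In the first two rows everyone at risk at month 18 has progressed. The smallest bias comes from PFS 55.9%, q = 15%, m = 24 (with the month-12 stop, true 0.790 against 0.735). The largest comes from PFS 69.9%, q = 5%, m = 9 (0.785 against 0.556).

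Just before month 24 the expected number at risk is under 0.1 of 49 in the first row and 0.5 to 1.3 in the second. No bias figure there is useful.

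**The case against.** The strongest objection is the second limit. If follow-up of progressed patients also ends one year after consolidation starts, all scheduled survival follow-up stops at month 12 and there is no asymmetry. One can reply that, for anyone who progresses after starting consolidation, progression + 12 months always falls later than month 12, so taking the earlier limit would leave the other with no work to do. But patients who progress before consolidation are barred from it by Section 3.3. They have no consolidation start date, so the limit counted from progression may be meant for them. Both readings are tenable. That part of the objection stands and makes the bias conditional.

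A reader might also infer that, after month 12, the curve rests only on progressed patients. The documents do not support that exactly. The D100 contact reaches about month 13.4, footnote 7 has no 12-month cap, and a progression found after month 12 also opens survival follow-up. These reduce the problem without removing it: crediting D100 still leaves 4.1 to 18.1 points at month 18, and footnote 7 depends on scans being available and schedules no survival contact.

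Finally, OS is not a listed endpoint, the 18- and 24-month landmarks in 12.6.1 concern progression, and the error runs against the regimen, so it cannot create a false positive signal. All of this stands and limits the importance of the point. It does not remove the need for a censoring rule where a formal OS comparison is planned.

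**Conclusion.** The point holds conditionally. Footnote 12 makes scheduled survival follow-up depend on progression and does not say which of two limits ends it. Under the limit counted from progression, the OS analyses in 12.6.1 are subject to informative censoring and biased low beyond about month 12 to 13.4. The size is roughly 4 to 23 points at month 18, on a handful of patients, and rests on assumed exponential PFS and post-progression medians of 9 to 24 months. Under the limit counted from the start of consolidation there is no bias, but there is also no OS estimate after month 12. Neither reading supports an OS curve for the cohort beyond about that time.

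A reader might infer that the trial's OS result is certainly biased, or that the primary result is compromised. The documents support neither: the first depends on an unresolved choice of limit, and the 12-month PFS estimate is not affected by this point. It should be repaired because the repair is nearly free.

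**What to change.** State in footnote 12 which limit governs, reconcile it with footnote 7, and use one end of survival follow-up for all patients whatever their progression status. Either option will do:

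- **Truncate OS.** Add one sentence to 12.6.1: OS is measured from consolidation cycle 1 day 1, all patients still alive are censored at 12 months, and no OS estimate is reported beyond that. This works whichever limit sites have applied. The cost is one sentence; the downside is no later OS.
- **Extend follow-up equally.** Amend footnote 12 so that survival status is collected in every patient, progressed or not, to one common date, for example 12 months after the last patient starts consolidation. Footnote 12 already permits telephone contact. The cost is a footnote amendment and one or two extra calls per progression-free patient. Kaplan-Meier OS is then free of this bias up to that date.
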